#### ***Definition of Adverse Reaction (AR)***

An adverse reaction (AR) is an AE, which is judged by the investigator as having a reasonable suspected causal relationship to an investigational medicinal product. For regulatory purposes an AR is an AE judged by either the investigator or the sponsor as having a reasonable suspected causal relationship to an investigational medicinal product. The expression reasonable causal relationship means to convey in general that there is evidence or argument to suggest a causal relationship.

#### ***Definition of Unexpected Adverse Reaction (UAR)***

An unexpected adverse reaction (UAR) is an AR, the nature and severity of which is not consistent with the applicable Nexavar® (Sorafenib) product information.

Examples of UAR include:

- An expected/ labeled AR with an unexpected outcome (e.g. a fatal outcome).
- A more specific reaction than labeled (“acute renal failure” is a labeled AR, a new report of “interstitial nephritis” is more specific and therefore unexpected).
- An increase in the rate of occurrence of an expected AR, which is judged to be clinically important, is considered as unexpected.

### ***Definition of Serious Adverse Event (SAE)***

A Serious Adverse Event (SAE) is any untoward medical occurrence (whether considered to be related to study drug or not) that occurs at any dose and:

- Results in death or
- Is life-threatening (at the time of the event; does not refer to an event which hypothetically might have caused death if it were more severe) or
- Requires in-patient hospitalization or prolongation of existing hospitalization (elective hospitalizations/procedures for preexisting conditions that have not worsened or for preplanned treatment are excluded) or
- Results in persistent or significant disability/incapacity or
- Is a congenital abnormality/birth defect.

Significant medical events that may or may not result in death, be life threatening, or require hospitalization, may also be considered as a serious adverse event when they may jeopardize the patient and may require medical or surgical intervention to prevent one of the outcomes in the definitions listed above.

All deaths including death to disease progression during protocol treatment and for 30 days after the last protocol treatment have to be reported immediately on an SAE form, although death is an outcome per definition, not an adverse event per se.

### ***Definition of Serious Adverse Reaction (SAR)***

A serious adverse reaction (SAR) is an SAE, which is judged by the investigator as having a reasonable suspected causal relationship to an investigational medicinal product. For regulatory purposes an SAR is an SAE judged by the sponsor as having a reasonable suspected causal relationship to an investigational medicinal product. The expression reasonable causal relationship means to convey in general that there is evidence or argument to suggest a causal relationship.

### ***Definition of Suspected Unexpected Serious Adverse Reaction (SUSAR)***

A suspected unexpected serious adverse reaction is an SAE, which is both judged by the investigator as having a reasonable suspected causal relationship to an investigational medicinal product (SAR) and the nature and severity of which is not consistent with the applicable Nexavar® (Sorafenib) product information. It is the duty of the sponsor to review all reported SAEs/ SARs for unexpectedness.

### ***Study specific exceptions***

Leukemia-associated serious adverse events do not have to be reported as serious adverse events on this protocol. Myelosuppression, thrombocytopenia, anemia and associated complications are expected events during leukemia therapy and are part of the treatment success (marrow emptying of leukemia cells). Therefore, myelosuppression-associated complications such as fever, infections, bleeding, and related hospitalization will be reported on appropriate pages of the CRF as an adverse event. In this context only prolonged myelosuppression, i.e. pancytopenia with marrow hypocellularity on day 40 or later from start of last cytotoxic therapy without evidence of leukemia, will require immediate reporting on an SAE form.

## **6.2 Safety monitoring and reporting of AEs**

AEs and SAEs will be recorded from the time the informed consent is signed, up to and including 30 days following last administration of study drug.

Severity of adverse events and serious adverse events will be graded according to the National Cancer Institute Common Terminology Criteria for Adverse Events (CTCAE) 3.0 for Cancer Clinical Trials.

All adverse events have to be recorded on the appropriate adverse event pages in the CRF.

The National Coordinating Investigator (LKP) is responsible for central safety monitoring and reporting on behalf of the sponsor and has installed a central safety desk located at the Studienzentrale SAL. The investigator must fax all serious adverse events (SAEs) identified by the protocol as requiring immediate reporting on an SAE form to the safety desk within 1 working day.

This applies regardless of severity (CTCAE 3.0 grade) and whether or not the SAE is considered related to the use of study drug by the investigator. Where possible, a diagnosis rather than a list of symptoms should be given. The investigator should complete all the details requested including dates of onset, severity, corrective therapies given, outcome and opinion as to whether the adverse event is likely to be drug-related. The investigator should not wait for full details before making the initial report. Personal data have to be replaced by the trial patient number before forwarding any information.

If the event is fatal or life threatening, the investigator must fax any relevant follow-up information of the reported SAE to the safety desk within additional 8 days. If the reported SAE is not fatal or life threatening, the investigator must fax follow-up information as soon as possible.

Via the central safety desk, the National Coordinating Investigator (LKP) will review the SAE again for seriousness and relatedness and assess the SAR for expectedness according to Summary of Product Characteristics Nexavar® Prescribing Information (Fachinformation).

Via the safety desk, the LKP will ensure that the Ethics Committee, competent authority and participating investigators will be informed of all suspected unexpected serious adverse reactions (SUSARs) and all other relevant safety information in accordance with legal requirements.

It is the duty of the safety desk to inform the marketing authorization holder of Sorafenib according to stipulation.

Safety Desk

Studienzentrale SAL

[name]

## **6.3 Warnings and Precautions**

### **6.3.1 Investigational product (Sorafenib)**

For the most recent safety update, please refer to the current Nexavar® Prescribing Information (Fachinformation).

#### **6.3.1.1 Contraindications**

Sorafenib is contraindicated in patients with known severe hypersensitivity to Sorafenib or any of the excipients.

#### **6.3.1.2 Special Warnings and Precautions for Use**

Nexavar® (Sorafenib) is approved for treatment of patients with hepatocellular carcinoma and advanced renal cell cancer. Because this is a novel agent, current knowledge of the adverse events associated with this compound is limited. As with any new chemical entity, there is always potential for unexpected adverse events.

**Pregnancy:** Women should avoid becoming pregnant while on therapy.

Women of childbearing potential must be apprised of the potential hazard to the fetus, which includes severe malformation (teratogenicity), failure to thrive and fetal death (embryotoxicity).

Sorafenib should not be used during pregnancy. Prescribers may only consider it to be used, if the potential benefits justify the potential risks to the fetus.

Based on the proposed mechanism of multikinase inhibition and multiple adverse effects seen in animals at exposure levels significantly below the clinical dose, Sorafenib should be assumed to cause fetal harm when administered to a pregnant woman.

Breastfeeding should be discontinued during Sorafenib therapy.

**Dermatological Toxicities:** Hand-foot skin reaction (palmar-plantar erythrodysesthesia) and rash represent the most common adverse drug reactions with Sorafenib. Rash and hand-foot skin reaction are usually CTC (National Cancer Institute Common Toxicity Criteria) Grade 1 and 2 and generally appear during the first six weeks of treatment with Sorafenib. Management of dermatologic toxicities may include topical therapies for symptomatic relief, temporary treatment interruption and/or dose modification of Sorafenib, or in severe or persistent cases, permanent discontinuation of Sorafenib.

**Hypertension:** An increased incidence of hypertension was observed in Sorafenib-treated patients. Hypertension was usually mild to moderate, occurred early in the course of treatment, and was amenable to management with standard antihypertensive therapy. Blood pressure should be monitored regularly and treated, if required, in accordance with standard medical practice. In cases of severe or persistent hypertension, or hypertensive crisis despite adequate antihypertensive therapy, permanent discontinuation of Sorafenib should be considered.

**Hemorrhage:** An increase in the risk of bleeding may occur following Sorafenib administration. The incidence of severe bleeding events is uncommon. If any bleeding event necessitates medical intervention, it is recommended that permanent discontinuation of Sorafenib be considered.

**Wound healing complications:** No formal studies of the effect of Sorafenib on wound healing have been conducted. In patients undergoing major surgical procedures, temporary interruption of Sorafenib therapy is recommended for precautionary reasons. There is limited clinical experience regarding the timing of reinitiation of therapy following major surgical intervention. Therefore, the decision to resume Sorafenib therapy following a major surgical intervention should be based on clinical judgment of adequate wound healing.

**Cardiac Ischemia and/or Infarction:** In the phase-III advanced RCC study (TARGETS), the incidence of treatment-emergent cardiac ischemia/infarction events was higher in the Sorafenib group (2.9%) compared with the Placebo group (0.4%). Patients with unstable coronary artery disease or recent myocardial infarction were excluded from this study. Temporary or permanent discontinuation of Sorafenib should be considered in patients who develop cardiac ischemia and/or infarction.

**Gastrointestinal perforation:** Gastrointestinal perforation is an uncommon event and has been reported in less than 1% of patients taking Sorafenib. In some cases this was not associated with apparent intra-abdominal tumor. Sorafenib therapy should be discontinued in patients with GI perforation.

**Effects on ability to drive and use machines:** No studies on the effects of Sorafenib on the ability to drive or use machines have been performed. There is no evidence that Sorafenib affects the ability to drive or operate machinery.

**Patients with Hepatic Impairment:** *In vitro* and *in vivo* data indicate that Sorafenib is primarily metabolized by the liver. Systemic exposure and safety data were comparable in patients with Child-Pugh A and B hepatic impairment. Sorafenib has not been studied in patients with Child-Pugh C hepatic impairment. No dose adjustment is necessary when administering Sorafenib to patients with Child-Pugh A and B hepatic impairment.

**Patients with Renal Impairment:** Sorafenib has not been studied in patients with severe renal impairment (CrCl <30 ml/min) or in patients undergoing dialysis.

**Carcinogenesis, Mutagenesis, Impairment of Fertility:** Carcinogenicity studies have not been performed with Sorafenib. Sorafenib was clastogenic when tested in an *in vitro* mammalian cell assay (Chinese Hamster Ovary) in the presence of metabolic activation. Sorafenib was not mutagenic in the *in vitro* Ames bacterial cell assay or clastogenic in an *in vivo* mouse micronucleus assay. One intermediate in the manufacturing process, which is also present in the final drug substance (<0.15%), was positive for mutagenesis in an *in vitro* bacterial cell assay (Ames test) when tested independently. No specific studies with Sorafenib have been conducted in animals to evaluate the effect on fertility. However, results from the repeat-dose toxicity studies suggest there is a potential for Sorafenib to impair reproductive performance and fertility. Multiple adverse effects were observed in male and female reproductive organs, with the rat being more susceptible than mice or dogs. Typical changes in

rats consisted of testicular atrophy or degeneration, degeneration of epidymidis, prostate, and seminal vesicles, central necrosis of the corpora lutea and arrested follicular development. Sorafenib-related effects on the reproductive organs of rats were manifested at daily oral doses  $\geq 30$  mg/m^2 (approximately 0.5 times the AUC in cancer patients at the recommended human dose). Dogs showed tubular degeneration in the testes at 600 mg/m^2/day (approximately 0.3 times the AUC at the recommended human dose) and oligospermia at 1200 mg/m^2/day of Sorafenib. Adequate contraception should be used during therapy and for at least 3 months after completing therapy.

**Pediatric Use:** The safety and effectiveness of Sorafenib in pediatric patients have not been studied. Repeat dosing of Sorafenib to young and growing dogs resulted in irregular thickening of the femoral growth plate at daily Sorafenib doses  $\geq 600$  mg/m^2 (approximately 0.3 times the AUC at the recommended human dose), hypocellularity of the bone marrow adjoining the growth plate at 200 mg/m^2/day (approximately 0.1 times the AUC at the recommended human dose), and alterations of the dentin composition at 600 mg/m^2/day. Similar effects were not observed in adult dogs when dosed for 4 weeks or less.

**Geriatric Use:** In total, 32% of RCC patients treated with Sorafenib were age 65 years or older and 4% were 75 and older. No differences in safety or efficacy were observed between older and younger patients, and other reported clinical experience has not identified differences in responses between the elderly and younger patients, but greater sensitivity of some older individuals cannot be ruled out.

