### 3.4 Removal of patients from study

A patient who withdraws is one who discontinues participation in a clinical study for any reason.

Patients may be withdrawn from the trial for the following reasons:

- At their own request or at the request of their legally acceptable representative
- If, in the investigator's opinion, continuation in the study would be detrimental to the patient's well-being
- At the specific request of the sponsor

Patients must be withdrawn also for the following reasons:

- In case of unacceptable toxicity or progressive disease
- In case of substantial non-compliance with the requirements of the study
- Positive beta-HCG test consistent with pregnancy. Pregnancy will be reported along the same time lines as a serious adverse event

- Use of illicit drugs or other substances that may, in the opinion of the investigator, have a reasonable chance of contributing to toxicity or otherwise skewing results
- Development of an intercurrent illness or situation which would, in the judgment of the investigator, affect assessments of clinical status and study endpoints to a significant degree
- Development of a second cancer that requires treatment
- Patient is lost to follow-up
- Interruption in study drug administration for a period longer than 28 consecutive days
- Patient death

Relevant visit data will be entered into the CRF, and any unused study medication will be accounted for and returned for all subjects entered into the trial even if for a brief period of time. Subjects who discontinue study treatment will have relevant information completed and recorded in the CRF and medical record. All subjects who discontinue because of adverse events or clinical laboratory abnormalities should be followed up until they recover or stabilize and the subsequent outcome recorded.

In case of premature withdrawal of any cause, all data documented up to the date of withdrawal will be entered into the study analysis.

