#### 4.1.5 Dose modification and delays of Sorafenib or Placebo

The modifications of Sorafenib or Placebo will follow the following pre-defined dose levels:

Dose level 1 (starting dose):	400 mg BID (2 tablets twice a day)
Dose level 2:	400 mg QD (2 tablets once a day)
Dose level 3:	400 mg QOD (2 tablets every second day)

Table 2: Sorafenib dose levels

Please note that the dose of 400 mg BID (total daily dose 800 mg) is the standard dose. If a dose reduction below 400 mg QOD (2 tablets every other day) is required, the patient should be discontinued from the study treatment. After resolution of the adverse event, the dose may be re-escalated from dose level 2 or 3 to the starting dose (see table) at the discretion of the investigator. As a general rule, grade 3 toxicity should be followed by permanent dose reduction. Exceptions are skin toxicities as defined below.

Resolution of an adverse event is defined as disappearance or reduction of the adverse event to below grade 3 toxicity. For patients with toxicities  $\geq$  grade 2 present at baseline (before start of Sorafenib/ Placebo treatment), resolution to maximum grade 1 level will apply.

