##### 4.1.5.1 Dose modification for hematological toxicity

Hematological toxicities will be considered not relevant for dose modification during the period of chemotherapy and the expected subsequent myelosuppression. However, these criteria will apply after hematopoietic recovery from the last chemotherapy course during the subsequent maintenance therapy.

Toxicity	Grade 1	Grade 2	Grade 3*	Grade 4*
Hematologic	Continue at the same dose level.	Continue at the same dose level.	Withhold dose until toxicity is grade <2, then resume treatment at the same dose level. If patient experiences a second grade 3 toxicity, withhold dose until toxicity is grade <2, then reduce dose to 400 mg p.o. QD and resume treatment.	Withhold dose until toxicity is grade <2, then reduce dose to 400 mg p.o. QD and resume treatment, or discontinue at the discretion of the principal investigator after discussion with study sponsor (safety desk at SAL).

\*Patients who develop grade 3 leukopenia, or grade 3/ grade 4 lymphopenia may continue Sorafenib/ Placebo treatment without interruption at the discretion of the investigator.

Table 3: Dose modifications and delays for hematologic toxicities of Sorafenib/ Placebo

Table 4 summarizes the recommendations for dose delays and modifications for all non-hematologic adverse events, except for skin toxicities and hypertension, which will be detailed separately (Table 5, Table 6, Table 7). These recommendations pertain, if the adverse event is considered to be related to Sorafenib/ Placebo, but not to the chemotherapy.

Toxicity	Grade 1	Grade 2	Grade 3*	Grade 4*
Non-hematologic	Continue at the same dose level.	Continue at the same dose level.	Withhold dose until toxicity is grade <1, then resume treatment at the same dose level. If patient experiences a second grade 3 toxicity, withhold dose until toxicity is grade <1, then reduce dose to 400 mg p.o. QD and resume treatment.	Withhold dose until toxicity is grade <1, then reduce dose to 400 mg p.o. QD. and resume treatment, or discontinue at the discretion of the principal investigator after discussion with study sponsor.

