*Patients who develop grade 3 fever/ chills, grade 3 elevation of hepatic transaminases with ALT and AST <10x ULN, grade 3 hyperlipasemia or hyperamylasemia without clinical or other evidence of pancreatitis may continue Sorafenib/ Placebo treatment without interruption at the discretion of the investigator. Also excludes nausea/ vomiting that has not been premedicated, and diarrhea. If no recovery after 30 day delay, treatment will be discontinued unless patient is deriving clinical benefit. If more than 2 dose reductions are required, treatment will be discontinued.				

*Table 4: Dose modifications for Sorafenib-associated non hematological toxicity except hand-foot skin reactions and hypertension*

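### Table 4 carries no exception for gastrointestinal perforation, so its literal advice after a drug-related grade 3 perforation departs from the stop instruction in section 6.3.1.2

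*Protocol*

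**What the plan says.** Two parts of the protocol address what to do with study drug after a gastrointestinal perforation.

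- **Section 6.3.1.2**, under its gastrointestinal perforation warning: "Sorafenib therapy should be discontinued in patients with GI perforation". No grade, occurrence or attribution is specified.
- **Section 4.1.5.1**, introducing Table 4: "Table 4 summarizes the recommendations for dose delays and modifications for all non-hematologic adverse events, except for skin toxicities and hypertension". The scope is then limited: "These recommendations pertain, if the adverse event is considered to be related to Sorafenib/ Placebo, but not to the chemotherapy".
- **Table 4, first grade 3 event**: "Withhold dose until toxicity is grade <1, then resume treatment at the same dose level". A second grade 3 event leads to resumption at 400 mg once daily.
- **Table 4, grade 4**: "Withhold dose until toxicity is grade <1, then reduce dose to 400 mg p.o. QD. and resume treatment, or discontinue", the last option being at the principal investigator's discretion once the sponsor has been consulted.
- **Section 4.1.5**, ahead of the tables: "As a general rule, grade 3 toxicity should be followed by permanent dose reduction".

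Section 3.4 lists reasons for removal. Among the mandatory ones is "In case of unacceptable toxicity or progressive disease", with no definition of unacceptable toxicity, and an interruption of study drug lasting more than 28 days. Among the optional ones is the investigator's opinion that staying in the study would harm the patient. Section 4.1.5.4 leaves restarting after major surgery to the clinician's view of how well the wound has healed.

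**The concern.** A site handling an adverse event will naturally turn to the dose-modification tables. A perforation attributed to study drug is a non-hematologic event, neither skin toxicity nor hypertension, so it falls under Table 4. For a first grade 3 event the table then advises a restart at full previous dose once the event has resolved, while the safety section says the drug should be stopped. Nothing in section 4.1.5 sends the reader to 6.3.1.2.

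What is at stake is the safety of an individual patient. Table 18 flags perforation among the events that can threaten life or prove fatal. The statistical design is not involved.

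**Working it through.** The point rests on comparing texts; the protocol states no figure for it that could be reproduced.

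**Step 1. What each rule gives for a perforation attributed to Sorafenib/Placebo and not to chemotherapy**

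| Rule | Situation | Literal outcome |
|---|---|---|
| 6.3.1.2 | Any grade | Discontinue |
| Table 4 | First grade 3 | Withhold to grade <1, resume at same dose |
| Table 4 | Second grade 3 | Withhold to grade <1, resume at 400 mg once daily |
| Table 4 | Grade 4 | Resume at 400 mg once daily, or discontinue |
| 4.1.5 general rule | Grade 3 | Permanent dose reduction |

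The first grade 3 cell gives the opposite of 6.3.1.2. The general rule in 4.1.5 disagrees with that cell about the dose, but it does not stop the drug either. At grade 4 the two texts can both be satisfied by choosing to discontinue; the inconsistency there is only that a restart is offered as well.

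**Step 2. Whether another rule makes stopping mandatory**

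- Unacceptable toxicity (3.4): mandatory, but undefined, so a perforation falls under it only if the investigator judges so.
- Interruption beyond 28 days (3.4): mandatory, but not reached if the event resolves sooner.
- The patient's well-being (3.4): available at any grade and for any cause, but permissive.
- Surgery (4.1.5.4): leaves the restart to judgment and does not mention the perforation warning.

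Each narrows the gap. None closes it.

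**Step 3. When Table 4 does not apply**

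An event put down to chemotherapy is outside the table. Section 4.2 lists severe ulceration of the gastrointestinal tract among the effects of high-dose cytarabine, so some perforations in this trial could be attributed that way.

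**Step 4. Upper bound on the number of patients**

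Inputs: 138 patients per arm (section 7.1, number of patients); perforation listed as uncommon in Table 18, above 0.1% and below 1%; section 6.3.1.2 also puts it below 1%.

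Expected perforations = patients × rate:

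- lower end: 138 × 0.001 = 0.138
- upper end: 138 × 0.01 = 1.38

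This counts all perforations. The conflict concerns only those attributed to study drug, of grade 3 (or grade 4 with the restart option taken), that resolve in time for a restart. The protocol gives nothing from which to estimate that share, so only the outer bound is reported.

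**The case against.** The strongest reply is that the protocol already gives the right instruction. Section 6.3.1.2 names the event, Table 4 is a generic grid that never mentions it, and a specific rule is ordinarily read ahead of a general one. Hemorrhage and cardiac ischemia also have warnings in 6.3.1.2 and no row in Table 4, so keeping event-specific advice there may simply be how the document is arranged. Much of this stands: a careful investigator would probably stop. But those two warnings only ask that discontinuation be considered, whereas the perforation warning is a plain instruction to stop. The skin, hypertension and surgery warnings do have counterparts in 4.1.5. No sentence says which text prevails.

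A reader might infer that sites are bound by two contradictory mandates, or are obliged to restart the drug. The documents do not support that. The protocol calls the content of Table 4 recommendations, and an investigator can stop under 6.3.1.2 or withdraw the patient under 3.4. The general duty in section 9.1.2 to follow the protocol does not turn a recommendation into an order to restart.

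A reader might also take the Table 4 footnote, which states "Also excludes nausea/ vomiting that has not been premedicated, and diarrhea", as evidence that perforation was overlooked among the gastrointestinal exceptions. That inference is weak. The footnote opens with events for which treatment may continue uninterrupted, and the gastrointestinal items follow on from that list. Perforation would not belong among relaxations, so its absence there shows little. The point rests on the table's scope and its grade 3 cell.

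Finally, the frequency band comes from single-agent use in cancer patients, while this trial gives the drug around intensive chemotherapy and then as maintenance. That limitation is accepted; the figures are an order of magnitude only.

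**Conclusion.** The inconsistency is real and minor. For a drug-related grade 3 perforation, the literal advice in Table 4 runs against the instruction in 6.3.1.2, and the general rule in 4.1.5 does not repair it. At grade 4 the table permits the right action without requiring it. Stopping is open to the investigator throughout and is the better reading, but section 4.1.5 neither points to it nor makes it mandatory.

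The size is at most about 0.14 to 1.4 expected perforations of any kind among 138 Sorafenib patients, assuming the single-agent rate carries over. The number actually exposed to the conflict is smaller by an amount the protocol does not allow one to state. There is no effect on alpha, power or sample size. Confidence is high for the comparison of texts; no claim is made that harm is likely.

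**What to change.** Add one row or footnote to Table 4: *GI perforation, any grade, regardless of attribution: discontinue Sorafenib/Placebo permanently (see 6.3.1.2).* Refer to it in section 4.1.5.4, so that a perforation treated surgically is not handled as an ordinary interruption for surgery.

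This wording also settles two smaller matters. It states the rule for blinded study drug, where 6.3.1.2 speaks only of Sorafenib. It also supplies the word permanent, which 6.3.1.2 uses for hypertension and hemorrhage but not for perforation.

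The cost is amendment wording only: no added visit, test or patient, and no change to the analysis.
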